9. Does not need to be repeated if previously performed.
10. CT scans and bone marrow biopsies may be performed within 7 days of the specified dates. Screening CT scans may be used if obtained as standard-of-care within 42 days prior to initiating treatment provided no prior therapy has been given. Screening bone marrow biopsies may, likewise, be used if obtained as standard of care within 90 days prior to initiating treatment provided no prior therapy has been given.

11. Overall response evaluations will be done every 12 weeks from randomization for the first 24 months, and then every 24 weeks. After Cycle 36, CT scan is yearly. Hematology results must be done within 7 days of CT scans. Bone marrow aspirates/biopsies to confirm complete response (CR) must be done within 4 weeks of the CT scan, which showed CR.
12. LN sample should also be sent for correlative studies at time of progressive disease/relapse, if performed as part of disease analysis.
13. EORTC QLQ-C30 will be assessed. See [Appendix 2](#).

A. At investigator decision subjects who are in CR or CR with incomplete bone marrow recovery (CRi) and/or MRD negativity may discontinue acalabrutinib after Cycle 24.

B. **CCI** [REDACTED]

C. Specific times and tube types of correlative samples are outlined in [Section 13.2](#).

D. As outlined in [Section 13.3](#). Drug and metabolite concentrations in plasma will be done by a bioanalytical contract research organization (CRO). **CCI** [REDACTED] Refer to the laboratory manual for instructions on collection and shipment of PK samples.

E. On Day 21, if indicated based on TLS risk.

F. To confirm CR, bone marrow aspirate/biopsy may be performed at any time. At time of bone marrow (BM) biopsy for CR confirmation, bone marrow should also be sent for correlative studies.

G. To confirm CR, draw PB for flow cytometry MRD at any time point if (i) PE/Lab/CT suggestive of CR OR (ii) there is lone residual splenomegaly and/or probable lone reactive lymphadenopathy in absence of other peripheral signs of residual CLL disease. If PB MRD is negative, in 2 to 3 months check BM biopsy/aspirate with BM MRD. If PB MRD is positive, PB MRD may be repeated q3 months until negative and then proceed to BM 3 months after negative PB MRD. Post-CR/CRi, PB MRD is completed every 6 cycles until PD (per [Hallek et al 2008](#)). Site may synchronize this activity with any protocol scheduled PB MRD if the blood draws are ± 2 months apart.

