4. Serum or urine HCG for women of child-bearing potential only.
5. Hepatitis serologies must include hepatitis B surface antigen (HBsAg), hepatitis B surface antibody (anti-HBs), hepatitis B core antibody (anti-HBc), and hepatitis C (HCV) antibody. In addition, any subjects testing positive for any hepatitis serology must have PCR testing (see exclusion criterion #16).
6. Subjects who are anti-HBc positive should have a quantitative PCR test for HBV DNA performed during screening. Subjects who receive combination therapy with an anti-CD20 monoclonal antibody (i.e., obinutuzumab) should have a quantitative PCR test monthly during treatment and until 12 months after the last dose of anti-CD20 therapy. After that, HBV PCR monitoring should continue quarterly (e.g., every 3 months) until at least 12 months after the last dose of acalabrutinib.
7. Laboratory evaluations must be performed on the date specified, \pm 3 days.
8. Does not need to be repeated at Screening if performed within 60 days of registration.
9. Does not need to be repeated if previously performed.
10. CT scans and bone marrow biopsies may be performed within 7 days of the specified dates. Screening CT scans may be used if obtained as standard-of-care within 42 days prior to initiating treatment provided no prior therapy has been given. Screening bone marrow biopsies may, likewise, be used if obtained as standard of care within 90 days prior to initiating treatment provided no prior therapy has been given.
11. Overall response evaluations will be done every 12 weeks from randomization for the first 24 months, and then every 24 weeks. After Cycle 36, CT scan is yearly. Hematology results must be done within 7 days of CT scans. Bone marrow aspirates/biopsies to confirm CR must be done within 4 weeks of the CT scan, which showed CR.
12. LN sample should also be sent for correlative studies at time of progressive disease/relapse, if performed as part of disease analysis.
13. EORTC QLQ-C30 will be assessed. See [Appendix 2](#).

A. At investigator discretion, subjects who are in CR or CRi and/or MRD negativity may discontinue acalabrutinib after Cycle 24.

B. **CCI**

C. Specific times and tube types of correlative samples are outlined in [Section 13.2](#).

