D. As outlined in [Section 13.3](#). Drug and metabolite concentrations in plasma will be done by a bioanalytical contract research organization (CRO). **CCI** Refer to the laboratory manual for instructions on collection and shipment of PK samples.

IRB PROTOCOL NUMBER: 2014C0140

OSU PROTOCOL: 14123

- E. On Day 21, if indicated based on TLS risk.
- F. To confirm CR, bone marrow aspirate/biopsy may be performed at any time. At time of bone marrow (BM) biopsy for CR confirmation, bone marrow should also be sent for correlative studies.
- G. To confirm CR, draw PB for flow cytometry MRD at any time point if (i) PE/Lab/CT suggestive of CR OR (ii) there is lone residual splenomegaly and/or probable lone reactive lymphadenopathy in absence of other peripheral signs of residual CLL disease. If PB MRD is negative, in 2 to 3 months check BM biopsy/aspirate with BM MRD. If PB MRD is positive, PB MRD may be repeated q3 months until negative and then proceed to BM 3 months after negative PB MRD. Post-CR/CRi, PB MRD is completed every 6 cycles until PD (per [Hallek et al 2008](#)). Site may synchronize this activity with any protocol scheduled PB MRD if the blood draws are ± 2 months apart.
- H. After disease progression, subjects will be contacted to assess survival status approximately every 12 weeks until death, withdrawal of consent by subject, lost to follow-up, or study terminated by sponsor, whichever comes first.
- I. If disease progression has not occurred at the time of the 30-day SFU, discontinuation follow-up visits should occur approximately every 12 weeks until disease progression. AE and concomitant medication reporting, irrespective of seriousness, ends 30 days after the last dose of study drug(s).
- J. CT scans should be performed every 24 weeks. After 2 years in discontinuation follow-up, CT scans will be performed annually.
- K. **CCI**

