14.6.2 Secondary Endpoints

All secondary endpoints will be evaluated for each cohort separately. The ORR of the combination therapy of acalabrutinib plus venetoclax plus an anti-CD20 antibody at Cycle 16 (Cohorts 3 and 4) will be calculated and 95% exact binomial CIs will be provided. The CR rate and MRD-negative CR rate will be summarized. The degree of response will be summarized as well as the number of subjects who achieve CR but remain positive for MRD. Duration of response, time to CR, PFS, TTNT, time to response, and OS will be summarized with simple descriptive statistics obtained using the Kaplan-Meier method. DOR will be measured from the date of initial response to the date of disease progression or death. PFS will be measured from the date of first treatment to date of disease progression or death. For DOR and PFS, subjects who do not have disease progression or death will be censored at the date of last disease assessment. Subjects receiving stem cell transplant will be censored at the date of last disease assessment prior to the transplant. Time to next anti-CLL treatment will be measured from date of first treatment until date of next treatment or death, censoring those alive who have not started another treatment at last follow-up. OS will be measured from date of first treatment until date of death or last follow-up. These analyses will be useful in planning future studies.

Cytogenetic and molecular marker data, including FISH and stimulated karyotype results, Zap-70 methylation, and IGHV mutational status will be summarized for all subjects.

Relationships between these baseline variables and response rate or PFS will be explored graphically (e.g., side-by-side boxplots or Kaplan-Meier plots), where estimates with CIs will be presented as the primary method of analysis due to the limited number of subjects. If given a sufficient number of events, baseline markers may be correlated with response or survival using logistic regression or proportional hazards models, respectively, and adjusting for subject cohort (i.e., treatment-naïve versus relapsed/refractory).

Correlative studies will assess the effects of acalabrutinib alone or in combination with other study drugs on **CCI** as well as B, T, and NK cell numbers over the course of therapy. With these data collected serially over time, patterns will be explored graphically using box plots and/or individual time plots as well as analytically with repeated measures analysis of variance.

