12.2.2 Complete Response Rate and MRD-Negative Complete Response Rate

The CR rate will be calculated and corresponding 95% confidence intervals through use of exact binomial distribution will be provided. The MRD-Negative CR rate will be summarized with MRD data in separate report..

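### Cohorts 3 and 4: three footnotes disagree on when, and on what condition, the marrow that confirms CR is taken, so blood-MRD-positive CRs may go unconfirmed and the CR rate may be too low

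*Protocol*

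**What the plan says.** For Cohorts 3 and 4, the marrow row in protocol Tables 12 and 13 is marked only at screening and at relapse or progression. An on-treatment marrow to confirm CR therefore rests on footnotes, worded essentially the same in both tables:

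- **Footnote 11** (response assessment row): "Bone marrow aspirates/biopsies to confirm complete response (CR) must be done within 4 weeks of the CT scan, which showed CR" in Table 12, and the same rule in Table 13.
- **Footnote F** (marrow row): "To confirm CR, bone marrow aspirate/biopsy may be performed at any time".
- **Footnote G** (MRD row, but opening with the purpose of confirming CR): draw blood MRD when exam, laboratory results and CT suggest CR, or when only residual splenomegaly or probably reactive nodes remain. Then "If PB MRD is negative, in 2 to 3 months check BM biopsy/aspirate with BM MRD". Otherwise "If PB MRD is positive, PB MRD may be repeated q3 months until negative and then proceed to BM", with the marrow 3 months after the negative result.

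No section says which footnote prevails. Protocol Section 9 requires for CR a marrow judged on morphology and immunohistochemistry, with all criteria held for at least 2 months. It sets no blood MRD criterion. Table 14 lists marrow as not assessed for PR.

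Protocol 14.6.2, which evaluates secondary endpoints by cohort, promises: "The degree of response will be summarized as well as the number of subjects who achieve CR but remain positive for MRD". SAP 12.2.2 says "The CR rate will be calculated and corresponding 95% confidence intervals through use of exact binomial distribution will be provided" and sends MRD-negative CR to a separate report. SAP 12.2.5 computes time to CR from a date of CR that it does not define. SAP 7.4 imputes no missing efficacy values.

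**The concern.** Footnote G is the only one of the three that sets out a step-by-step work-up, and it contains no marrow step while blood MRD stays positive. A site that treats it as the operating procedure would not send such a subject for marrow. Without a marrow, CR cannot be assigned. PR needs no marrow, so the subject is recorded as PR, and the SAP has no category that separates this case from a true PR.

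CR rate and time to CR are secondary objectives for all cohorts, and the count of CRs that remain MRD-positive is a promised summary. All three could then depend on which footnote the site followed. In Cohorts 1 and 2, Table 11 footnote B sets the 4-week rule with no blood MRD step, so CR might also be ascertained differently between the two pairs of cohorts.

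**Working it through.** The documents give no CR rate, no MRD-positive share and no adherence figure for Cohorts 3 and 4, so there is no plan figure to reproduce. Two checks can be made.

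**1. Timing.** Inputs: the 4-week limit (28 days) from footnote 11; the delays in footnote G; 30.4375 days per month (SAP 6.3); CTs every 12 weeks to month 24 and every 24 weeks after that (footnote 11). Assumption: blood MRD is drawn on the day of the CT that suggests CR (day 0).

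- Blood MRD negative: marrow at 2 × 30.4375 = 61 days to 3 × 30.4375 = 91 days. Excess over the limit: 61 − 28 = 33 days to 91 − 28 = 63 days.
- One positive draw, then a negative repeat at 3 months: marrow at 6 × 30.4375 = 183 days, about 26 weeks.
- Against the next CT under 12-weekly imaging (day 84): from 84 − 61 = 23 days before to 91 − 84 = 7 days after. This is within 4 weeks of a later CT, if that CT still shows CR.
- Against the next CT under 24-weekly imaging (day 168): 168 − 91 = 77 to 168 − 61 = 107 days before. This cannot be reconciled with 4 weeks.

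**2. Effect on the CR rate.** Inputs: n = 12 per cohort (protocol 14.2) and the All Treated denominator (SAP 12.2). Let *f* be the share of true CRs that are blood-MRD-positive and *u* the share of those that never get a marrow. Then

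observed CR rate = true CR rate × (1 − *f* × *u*).

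One missed CR costs 1/12 = 8.3 points. For an assumed 6 true CRs, with exact (Clopper-Pearson) 95% intervals:

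| Missed | Reported CR | 95% CI |
|---|---|---|
| 0 | 6/12 = 50.0% | 21.1 to 78.9% |
| 1 | 5/12 = 41.7% | 15.2 to 72.3% |
| 2 | 4/12 = 33.3% | 9.9 to 65.1% |
| 3 | 3/12 = 25.0% | 5.5 to 57.2% |

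Over assumed true CR rates of 25% to 75% and *f* of 10% to 50%:

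- *u* = 1 (G is a strict gate and blood MRD never clears): shortfall from 0.25 × 0.10 = 2.5 points to 0.75 × 0.50 = 37.5 points.
- *u* = 0.5: half of that.
- *u* = 0 (F or 11 followed): zero.

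In the row with 2 missed, suppose the other 4 CRs are MRD-negative. The MRD-negative CR rate over all treated subjects is 4/12 either way. Only the share among confirmed CRs moves, from 4/6 to 4/4, and that share is not a planned endpoint.

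**The case against.** A reader might infer that MRD-positive CRs cannot be confirmed in these cohorts and that the CR rate is biased down by design. The documents do not support that. Footnote F permits the marrow and footnote 11 requires it, neither with an MRD condition. G is permissive about repeating the blood test and is attached to the MRD row, so it can be read as governing only when marrow MRD is checked. Subjects who are blood-negative but marrow-positive still reach marrow under G, and those who clear later are delayed rather than lost. Nor is the MRD-negative CR rate shown to be biased, because those subjects pass through G.

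The timing conflict is also narrower than it looks. A 2-to-3-month wait fits the 2-month persistence that CR requires, and under 12-weekly imaging the marrow falls close to the next CT. G's second trigger covers subjects whose CT may not have shown CR, to whom footnote 11 would not apply. Finally, the primary objective in Cohorts 3 and 4 is safety, Cycle 16 ORR counts PR as response, and SAP 7.1 plans no formal tests, so no planned comparison with Cohorts 1 and 2 is affected.

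All of this stands, and it limits the point to a conditional one. It does not remove the conflict. G states that its purpose is to confirm CR, its negative branch misses the 4-week limit counted from the CT that triggered it, and persistently blood-positive subjects have no route to marrow within G.

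**Conclusion.** The three footnotes conflict, and the SAP does not say how a clinical and CT CR without marrow is handled. If G is followed as a gate, the CR rate in Cohorts 3 and 4 may be too low by 8.3 points per unconfirmed subject, time to CR may be too long, and the count of CRs that remain MRD-positive may be too small. If F or 11 is followed, the loss in CR rate is zero. The actual size cannot be determined from the documents; the ranges above rest on assumed CR rates, MRD-positive shares and site practice. Cycle 16 ORR, the primary safety objective and the MRD-negative CR rate over all treated subjects are not shown to be biased. This is a cheap clarification worth making, not a flaw in the main objective.

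**What to change.** **Protocol, Tables 12 and 13.** The sponsor must reconcile footnotes 11, F and G and state whether CR confirmation depends on blood MRD, consistently with the CR definition in Section 9. Which marrow schedule applies is a clinical choice for the sponsor; CR status also bears on stopping acalabrutinib (footnote A). The SAP describes these cohorts as already enrolled, so this may come too late for some assessments. The SAP changes help whichever footnote was followed.

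**SAP 12.2.2, Cohorts 3 and 4.** Report subjects who meet all exam, count and CT criteria for CR but have no confirmatory marrow as a separate row, with blood MRD status where available. Give the CR rate without them as the main result and with them as a sensitivity result, both with exact 95% intervals. The second is an upper figure, since some of these marrows might not have confirmed CR. Read the CR-but-MRD-positive count, wherever it is reported, alongside that row.

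**SAP 12.2.5.** State which date is the date of CR and apply it the same way in all cohorts.

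**Cost.** Wording, one extra table row and a CR rate shown two ways. The SAP part needs no further procedure on any subject.

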8.1 Pre-Treatment (Screening) Evaluation

Subjects will be evaluated prior to registration after signing informed consent. Laboratory evaluations and ECG must be done within 14 days, CT scans within 42 days, and bone marrow within 90 days provided no prior therapy has been given. Therapy must begin within 28 days following registration. Required pre-treatment evaluation includes:

- History and physical examination, including medication reconciliation, weight, ECOG performance status, and clinical tumor measurement
- ECG
- Complete blood count (CBC) with differential
- Chem 10 panel
- Lactate dehydrogenase (LDH)
- Uric acid
- Calculated CrCl
- ALT/AST, total and direct bilirubin, albumin, total protein, alkaline phosphatase
- Direct antiglobulin (Coomb's test)
- Quantitative immunoglobulins
- Peripheral blood flow cytometry
- Beta 2 microglobulin
- Zap-70 methylation
- Stimulated karyotype and FISH analysis (CLL panel) on either blood or bone marrow (required within 60 days of registration)
- CLL mutational screen
- CT scans of chest/abdomen/pelvis including index lesion measurement
- Bone marrow biopsy with pathology evaluation and flow cytometry
- Psychological/behavioral measures [Section 13.4](#)

8.2 Study Evaluations

The schedule of required procedures for each cycle is detailed in the tables in [Section 8](#). Laboratory evaluations must be performed on the date specified and within the window specified in [Section 8](#). CT scans and bone marrow biopsies may be performed within 7 days of the specified dates. Clinical evaluations and laboratory studies may be repeated more frequently if

clinically indicated. Such unscheduled assessments will be captured in the protocol-specific database as appropriate.

Radiological imaging by CT with contrast is required and must include the pelvis, abdomen, chest, and neck. Subjects who are intolerant to IV CT contrast agents will have CT scans performed with oral contrast. MRI may be used for imaging assessments if a contrast CT scan is contraindicated or unobtainable (in cases where MRI is desirable, the MRI must be obtained at baseline and at all subsequent response evaluations).

8.3 Safety Follow-up

Each subject should be followed until the safety follow-up (SFU) visit at 30 (+7) days after his or her last dose of all study drug(s) to monitor for resolution or progression of AEs and to document the occurrence of any new events, regardless of whether the subject receives a new anticancer therapy or demonstrates disease progression within this timeframe. Subjects who withdraw consent for study treatment should still be encouraged to complete the Safety Follow-up assessments before withdrawing consent, but these assessments cannot be mandated if subject consent for further study participation is withdrawn. The Schedule of Activities ([Section 8](#)) describes the procedures required for the Safety Follow-up visits.

8.4 Discontinuation Follow-up

After discontinuation of study treatment for any reason (except for death, lost to follow up, or withdrawal of consent), each subject should be followed until disease progression. If disease progression has not occurred at the time of the 30-day SFU visit, discontinuation follow-up visits should occur approximately every 12 weeks until disease progression. During this period, subjects will be followed via CT scans (every 24 weeks), CBC with differential, physical examinations (including vital signs and weight), serum chemistry, peripheral blood MRD (every 6 months for subjects in Cohorts 3 and 4 who will be monitored while off study drugs), and bone marrow biopsy and aspirate (as clinically indicated); after 2 years in discontinuation follow-up, CT scans will be yearly. Refer to the Schedule of Assessments ([Section 8](#)) for a full list of assessments required during this period.

8.5 Long-Term Follow-up

After disease progression, subjects will be contacted to assess survival status approximately every 12 weeks until death, withdrawal of consent by subject, lost to follow-up, or study terminated by sponsor, whichever comes first.

9 Criteria for Response, Progression, and Relapse

Any subject who has confirmed objective evidence of cancer progression while receiving regimens of acalabrutinib and obinutuzumab; acalabrutinib, venetoclax, and obinutuzumab; or

acalabrutinib, venetoclax, and rituximab should be withdrawn from the study treatment. If there is uncertainty regarding whether there is true cancer progression, the subject may continue study treatment and remain under close observation (e.g., evaluated at 4-week intervals) pending confirmation of progression. In particular, transient worsening of disease early in therapy or during temporary interruption of study therapy (e.g., for drug-related toxicity, surgery, or intercurrent illness) may not indicate cancer progression. In such circumstances, and if medically appropriate, subjects may resume therapy and relevant clinical, laboratory, and/or radiologic assessment can be attempted to document whether tumor control can be maintained or whether cancer progression has occurred.

Criteria for response for CLL and prolymphocytic leukemia (PLL) will utilize the IWCLL 2008 ([Hallek et al. 2008, Table 14](#)) for response, which includes clinical, hematologic, and bone marrow features. Responses will be classified as follows:

Complete response: Requires all of the following for a period of at least 2 months:

- Absence of lymphadenopathy >1.5 cm on physical examination and CT scan
- No hepatomegaly or splenomegaly on physical examination (a CT scan also may be used to assess)
- Normal CBC as exhibited by polymorphonuclear leukocytes $\geq 1,500/\mu\text{L}$, platelets $>100,000/\mu\text{L}$, hemoglobin $>11.0\text{ g/dL}$ (untransfused); absolute lymphocyte count $<4,000/\mu\text{L}$
- Bone marrow aspirate and biopsy must be normocellular for age with $<30\%$ of nucleated cells being lymphocytes. Lymphoid nodules may be present but must be T-cell in origin. If these are demonstrated to be clonal B-cells, subjects should be considered to be a PR. Additionally, if bone marrow is positive by immunohistochemistry (IHC) for CLL cells, it should be considered a PR. If the marrow is hypocellular a bone marrow should be performed in 2 to 3 months. If blood counts (polymorphonuclear leukocytes $<1,500/\mu\text{L}$, platelets $<100,000/\mu\text{L}$) fail to recover at the time of the response evaluation but there is otherwise no evidence of CLL, a repeat determination should be performed at the time of count recovery (polymorphonuclear leukocytes $\geq 1,500/\mu\text{L}$, platelets $>100,000/\mu\text{L}$) but should not exceed 6 months.
- Subjects who fulfill the criteria for CR with the exception of a persistent cytopenia (i.e., anemia, thrombocytopenia, or neutropenia) that is believed to be unrelated to CLL but related to drug toxicity will be considered a CR with incomplete marrow recovery (CRi). As stated above, subjects falling into this category should ideally undergo a repeat bone marrow when counts recover fully. If the bone marrow at full count recovery reveals no CLL, these subjects will be considered to be in complete remission at that time.
- Subjects who fulfill the criteria of CR with exception of having bone marrow lymphoid CLL nodules will be considered a nodular PR (nPR), and assessed prospectively for similarity to outcome with CR.

Partial Response: Requires a $\geq 50\%$ decrease in peripheral lymphocyte count from pre-treatment value or absolute lymphocyte count $< 5,000/\mu\text{L}$, $\geq 50\%$ reduction in lymphadenopathy of as many as 6 measurable lymph nodes, and/or $\geq 50\%$ reduction in splenomegaly/hepatomegaly for a period of at least 2 months. Additionally, these subjects must have 1 of the following:

- Polymorphonuclear leukocytes $\geq 1,500/\mu\text{L}$ or 50% improvement from pre-treatment value
- Platelets $> 100,000/\mu\text{L}$ or 50% improvement from pre-treatment value
- Hemoglobin $> 11.0 \text{ g/dL}$ (untransfused) or 50% improvement from pre-treatment value
- Subjects who meet the criteria for PR with the exception of having less than a 50% reduction in peripheral lymphocyte count AND absolute lymphocyte count $> 5,000/\mu\text{L}$ will be considered a PRL. These subjects should continue to be followed on therapy and response status updated if the lymphocyte count does decrease by $\geq 50\%$ or absolute lymphocyte count $< 5,000/\mu\text{L}$ is achieved.

Progressive Disease: Progressive disease will be characterized by any one of the following events:

- $\geq 50\%$ increase in the products of at least 2 lymph nodes on 2 consecutive determinations 2 weeks apart (at least 1 lymph node must be $\geq 2 \text{ cm}$); appearance of new palpable lymph nodes
- $\geq 50\%$ increase in the size of the liver and/or spleen as determined by measurement below the respective costal margin; appearance of palpable hepatomegaly or splenomegaly, which was not previously present
- Transformation to a more aggressive histology (i.e., Richter's syndrome or PLL with $\geq 56\%$ prolymphocytes)
- The progression of any cytopenia (unrelated to autoimmune cytopenia), as documented by a decrease of Hgb levels $> 2 \text{ g/dL}$ or to $< 10 \text{ g/dL}$, or by a decrease of platelet counts $> 50\%$ or to $< 100,000/\mu\text{L}$, which occurs at least 3 months after the initiation of treatment, defines disease progression, if the marrow biopsy demonstrates an infiltrate of clonal CLL cells. During therapy, cytopenias cannot be used to define disease progression.

Stable Disease: Subjects who do not fulfill the criteria for CR or PR as defined above but do not exhibit progressive disease will be considered as having stable disease (SD).

Table 14: IWCLL Response Assessment Criteria

Response	Lymphocytes	Bone Marrow	Physical Examination ^a (Nodes, Liver, Spleen)	Peripheral Blood
CR*	Lymphocytes $<4 \times 10^9/L$	Normocellular $<30\%$ lymphocytes No B-lymphoid nodules	Normal (e.g., no lymph nodes >1.5 cm)	ANC $>1.5 \times 10^9/L^b$ Platelets $>100 \times 10^9/L^b$ Hemoglobin >11.0 g/dL (untransfused) ^b
CRi	Lymphocytes $<4 \times 10^9/L$	Hypocellular $<30\%$ lymphocytes	Normal (e.g., no lymph nodes >1.5 cm)	Persistent anemia, thrombocytopenia, or neutropenia related to drug toxicity
nPR	CR with the presence of lymphoid nodules in the bone marrow, which reflect residual disease			
PR*	Lymphocytes $<5 \times 10^9/L$ Or $\geq 50\%$ decrease from baseline	Not assessed	$\geq 50\%$ reduction in lymphadenopathy ^c and/or in spleen or liver enlargement	ANC $>1.5 \times 10^9/L$ Or Platelets $>100 \times 10^9/L$ or 50% improvement over baseline ^b Or Hemoglobin >11.0 g/dL or 50% improvement over baseline (untransfused) ^b
PRL*	Lymphocytes $\geq 5 \times 10^9/L$	Not assessed	$\geq 50\%$ reduction in lymphadenopathy ^c and/or in spleen or liver enlargement	ANC $>1.5 \times 10^9/L$ Or Platelets $>100 \times 10^9/L$ or 50% improvement over baseline ^b Or Hemoglobin >11.0 g/dL or 50% improvement over baseline (untransfused) ^b
SD	Absence of PD and failure to achieve at least a PR			
PD*	Lymphocytes $\geq 50\%$ increase over baseline	Not assessed	Appearance of any new lesion or de novo appearance of hepatomegaly or splenomegaly Or Increase $\geq 50\%$ in lymphadenopathy Or Increase $\geq 50\%$ in hepatomegaly or splenomegaly	Platelets decrease of $\geq 50\%$ from baseline secondary to CLL Or Hemoglobin decrease of >2 g/dL from baseline secondary to CLL

Modified from Hallek et al. 2008.

ANC = absolute neutrophil count; CLL= chronic lymphocytic leukemia; CR = complete remission (response); CRi = CR with incomplete bone marrow recovery; nPR = nodular partial remission; PD = progressive disease; PR = partial remission (response); PRL = partial remission (response) with lymphocytosis; SD = stable disease

*CR: all of the above CR criteria have to be met, and subjects have to lack disease-related constitutional symptoms; PR: at least two of the above PR criteria for lymphadenopathy, splenomegaly, hepatomegaly, or lymphocytes plus one of the criteria for ANC, platelets or hemoglobin have to be met; PRL: presence of lymphocytosis, plus $\geq 50\%$ reduction in lymphadenopathy and/or in spleen or liver enlargement, plus one of the criteria for ANC, platelets or hemoglobin have to be met; PD: at least one of the above PD criteria has to be met, or transformation to a more aggressive histology (e.g., Richter's syndrome). Note: Isolated elevation of treatment-related lymphocytosis by itself will not be considered PD unless subject becomes symptomatic from this per Cheson et al 2012.

- a. Computed tomography (CT) scan of abdomen, pelvis, and thorax may be used if previously abnormal
- b. Without need for exogenous growth factors
- c. In the sum products of ≤ 6 lymph nodes or in the largest diameter of the enlarged lymph node(s) detected before therapy and no increase in any lymph node or new enlarged lymph nodes

Response criteria for SLL subjects will use 2007 Revised Response Criteria for Malignant Lymphoma ([Cheson et al. 2007](#)). Responses will be classified as follows:

Complete response: Requires all of the following:

- Complete absence of all detectable clinical evidence of disease and disease-related symptoms present prior to therapy
- Regression of lymphadenopathy to normal size (≤ 1.5 cm) on physical examination and CT scan. Previously involved nodes that were 1.1 to 1.5 cm in long axis and more than 1 cm in short axis must have decreased to ≤ 1 cm in their short axis.
- No hepatomegaly or splenomegaly on physical examination or CT scan, and nodules related to lymphoma should disappear.
- Bone marrow aspirate and biopsy must be free of disease on an adequate biopsy sample. If indeterminate by morphology, IHC must be negative.

Partial Response: Requires all of the following:

- $\geq 50\%$ decrease in sum of product of the diameters of up to 6 largest dominant masses. No increase in size of other nodes and no new lesions.
- $\geq 50\%$ reduction in sum of product diameters of nodules in spleen/liver with no increase in size of liver or spleen.

Progressive Disease: Progressive disease will be characterized by any 1 of the following events:

- Appearance of a new lesion > 1.5 cm in any axis
- $\geq 50\%$ increase in the products of at least 2 lymph nodes
- $\geq 50\%$ increase in the longest diameter of a previously identified node > 1 cm in short axis
- $\geq 50\%$ increase in the size of the liver and/or spleen or previously determined nodules in the liver or spleen
- New or recurrent bone marrow involvement

Stable Disease: Subjects who do not fulfill the criteria for complete or partial response as defined above but do not exhibit progressive disease will be considered as having SD.

10 Patient Safety and Adverse Event Reporting

